7.2.4 Coagulation and Inflammation Biomarkers

The following laboratory parameters will be collected and analyzed by a central laboratory. Change from baseline to both Day 8 or discharge will be summarized for inflammatory biomarkers (IL-6, hsCRP) and coagulation biomarkers (PT, PTT, factor Xa and tissue factor). All data will be listed. Primary analyses will be by Wilcoxon-family tests as described above in the primary efficacy endpoint. For purposes of interpretation of outcomes, IL-6 and hsCRP are considered measures of systemic inflammation, PT, PTT and factor Xa are coagulation parameters, and tissue factor is the biologic target of rNAPc2. In addition,

in a subset of participants anti-phospholipid antibodies known to be generated in COVID-19 and inhibited by rNAPc2, are being measured at baseline, Day 8/discharge and on Day 30 at a specialty laboratory.

7.3 Exploratory Efficacy Endpoints

7.3.1 Composite of All-Cause Mortality and Thrombotic Events

Time to first occurrence of a composite of all-cause mortality and any adjudicated thrombotic event within 30 days of randomization and time to all-cause mortality within 30 days of randomization will be analyzed by the same methods as described for ACTT above, with the exception that deaths will be counted as an event. Participants without an adjudicated event by Day 30 will be censored on the study day of last contact or Day 30, whichever is earlier. There will be no censoring prior to Day 30 due to study treatment discontinuation or initiation of non-study treatment.

7.3.2 Healthcare Resource Utilization

Days in intensive care unit, on ventilator, vasopressors, renal replacement therapy, and circulatory support will be summarized with descriptive statistics.

Organ support free days will be compared between the rNAPc2 and heparin arms via Wilcoxon Rank Sum testing, as in analysis of the Primary Efficacy Endpoint. Organ support free days is defined as total number of days without any of the following: placement on invasive mechanical ventilation, intravenous inotrope or vasopressor administration, renal dialysis, mechanical circulatory support, or death will be documented for each patient, and the number of total as well as individual interventions per patient will be compared by treatment group. Subjects who die are assigned a score of -1 for organ support free days. In the event that a large number of ties exist (e.g., a substantial proportion of subjects have the entire 30 days free of organ support), then organ support free days will be categorized as 30, 0-29, and -1 representing no organ support needed, some organ support needed, and death, respectively. An equivalent scenario involving every day requiring organ support for many subjects would yield 1-30, 0, -1 as categories. This tabulation will be analyzed subsequently using an Exact Wilcoxon test, such that ordinality across categories is maintained. In a circumstance where only two of the three categories are observed, this becomes an exact binomial test.

7.3.3 Post-COVID Functional Status

Post-COVID Functional Status (PCFS) score at discharge and Day 30 will be summarized with descriptive statistics.

7.4 Significance

All statistical tests and confidence intervals will use a 2-sided analysis with a significance level of $\alpha = 0.05$.

8 Safety Analysis

The following safety analyses will be based on the Safety population and on-treatment data scope. Additional safety analyses are detailed in [Section 11.4](#).

8.1 Primary Safety Endpoint

The primary safety endpoint is major or non-major clinically relevant bleeding through the earliest of Day 8 or two days after Day of Discharge if prior to Day 8.

The frequency and percentage of participants with major or non-major clinically relevant bleeding within 8 days of randomization as adjudicated by the CEC will be presented by each rNAPc2 dose and any heparin dose.

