3 OBJECTIVES AND ENDPOINTS

OBJECTIVES	ENDPOINTS	JUSTIFICATION FOR ENDPOINTS
Phase 2b- Safety		
The Phase 2b safety objective is to identify an rNAPc2 dosing regimen with an acceptable bleeding profile compared to SoC heparin regimens	
Primary safety endpoint: major or non-major clinically relevant bleeding (Section 8.3 Safety and Other Assessments) within eight (8) days of randomization as compared to heparin
 
Secondary safety endpoints are:
 
 major or non-major clinically relevant bleeding with rNAPc2 vs. heparin bleeding with higher vs. lower dose rNAPc2 through Day 30 Other AEs 	Both rNAPc2 and heparin cause bleeding
Phase 3 – Safety		
The Phase 3 safety objective is to assess tolerability of rNAPc2 compared with heparin	
Primary safety endpoint: major or non-major clinically relevant bleeding within eight (8) days of randomization as compared to heparin (Section 8.3 Safety and Other Assessments)
 
Secondary safety endpoints are:
 
 major or non-major clinically relevant bleeding with rNAPc2 vs. heparin through Day 30 	Both rNAPc2 and heparin cause bleeding

OBJECTIVES	ENDPOINTS	JUSTIFICATION FOR ENDPOINTS
	
 Other AEs 	
Phase 2b – Primary efficacy		
The primary efficacy objective is to identify a rNAPc2 dosing regimen which reduces D-dimer levels compared to SoC heparin regimens	Primary efficacy endpoint: change in D-dimer level from baseline to Day 8, or day of discharge if prior to Day 8	D-dimer reflects the rNAPc2 mechanism of action and predicts survival in patients with COVID-19
Phase 2b – Secondary and exploratory		

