6.3 MEASURES TO MINIMIZE BIAS: RANDOMIZATION AND BLINDING

Intervention Allocation

Site-based randomization will be implemented in this study. Participants will be randomly assigned to treatment groups based on a computer-generated randomization schedule prepared before the study by or under the supervision of the Sponsor. The randomization will be balanced by using randomly permuted blocks for each site and the D-dimer level stratification. After confirming eligibility, the requestor will obtain the participant's randomization assignment.

Blinding

To minimize the potential for bias, data that may potentially unblind the intervention assignment will be handled with special care to maintain the integrity of blinding for the participant and the CEC. This includes discouraging speculation and avoiding verbal disclosure to the participant and redacting the

data in question from medical records reviewed by the CEC. Study site investigators assessing potential clinical efficacy and safety events should be blinded to treatment allocation, if possible. Neither the study site, Sponsor, CEC, nor study participants will have access to the central laboratory results during the conduct of the trial with the exception of clinical safety alerts.

The investigator will not be provided with randomization codes. The study site will know the treatment assignment, however; participants should not be made aware of their treatment assignment.

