8.3 SAFETY AND OTHER ASSESSMENTS

Safety assessments will include monitoring of serious and non-serious AEs and study endpoints. Efficacy and safety endpoints, including all bleeding events, will not be considered as AEs or SAEs (see [Section 8.4 Adverse Events and Serious Adverse Events](#)). Safety evaluations will be assessed by the investigator per the SoA via EMR review, telephone or web contact with the participant or their health care provider.

Safety Events:

Bleeding events are considered safety endpoints for the study.

The study will classify bleeding events as major, non-major clinically relevant or non-major non-clinically relevant. Safety endpoints for this study include major, critical site and fatal bleeding and non-major clinically relevant bleeding using modified International Society on Thrombosis and Haemostasis (ISTH) bleeding criteria. All bleeding events will be assessed, classified and reported by the investigator in the eCRF. Major bleeding events will be adjudicated by the CEC.

An ISTH major bleeding event is defined as overt bleeding that is associated with:

- A fall in hemoglobin of 2 g/dL (1.24 mmol/L) or more, or
- A transfusion of 2 or more units of packed red blood cells or whole blood, or
- A critical site: intracranial, intraspinal, intraocular, pericardial, intra-articular, intramuscular with compartment syndrome, retroperitoneal, or
- A fatal outcome.

Non-major clinically relevant bleeding is defined as overt bleeding not meeting the criteria for major bleeding but associated with medical intervention, unscheduled visit or telephone call with a healthcare provider or temporary or permanent cessation of study treatment or associated with discomfort for the participant such as pain or impairment of activities of daily life.

Bleeding events not meeting the definition of major or non-major clinically relevant bleeding will be classified as non-major, non-clinically relevant.

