2.4.2 Safety

The primary safety endpoint is major or non-major clinically relevant bleeding within eight (8) days of randomization as compared to heparin.

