8.2 Secondary Safety Endpoints

8.2.1 Major or non-major clinically relevant bleeding through Day 30

The frequency and percentage of participants with major or non-major clinically relevant bleeding through Day 30 as adjudicated by the CEC will be presented by each rNAPc2 dose and heparin dose (pooled and via characteristics, i.e., Prophylactic vs. Therapeutic, Unfractionated vs Low Molecular Weight).

8.2.2 Any bleeding through Day 8 and through Day 30

The frequency and percentage of participants with any bleeding major, non-major clinically relevant, non-major and not clinically relevant as defined in the protocol) through Day 8 and through Day 30 will be presented by each rNAPc2 dose and heparin dose (pooled and via characteristics, i.e., Prophylactic vs Therapeutic, Unfractionated vs. Low Molecular Weight).

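### SAP 8.1 gives the primary bleeding endpoint two different windows, and SAP 8.3 takes liver tests from the central laboratory although the current protocol collects them only locally

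*SAP*

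**What the plan says.** **Window.** SAP 8.1 contains two adjacent statements. The first defines the endpoint as "major or non-major clinically relevant bleeding through the earliest of Day 8 or two days after Day of Discharge if prior to Day 8". The second promises counts and percentages of participants with "major or non-major clinically relevant bleeding within 8 days of randomization as adjudicated by the CEC". SAP 2.4.2 has "major or non-major clinically relevant bleeding within eight (8) days of randomization as compared to heparin", and protocol section 3 has "major or non-major clinically relevant bleeding (Section 8.3 Safety and Other Assessments) within eight (8) days of randomization as compared to heparin"; protocol 4.1 agrees with both. SAP Section 12, which lists departures from the protocol, does not mention a discharge-based cut-off.

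**Data scope.** The opening of SAP Section 8 adds: "The following safety analyses will be based on the Safety population and on-treatment data scope". SAP 5.2 ends that scope 72 hours after study drug is permanently stopped, and moves only the Day 30 bleeding endpoints to a different scope.

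**Liver tests.** SAP 8.3 summarises AST, ALT and bilirubin, and screens for Hy's law, under a central-laboratory label. In the current protocol, Table 2b (central samples) does not include these tests, and 8.1.2 lists them among the local values.

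**Event source.** SAP 8.1 and 8.2.1 count both bleeding classes as CEC-adjudicated; 8.2.1 reads "major or non-major clinically relevant bleeding through Day 30 as adjudicated by the CEC". Protocol 8.3 has the investigator classify every bleed and then specifies adjudication for one class: "reported by the investigator in the eCRF. Major bleeding events will be adjudicated by the CEC".

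**The concern.** An acceptable bleeding profile against heparin is part of the Phase 2b primary objective, and Phase 2b data select the Phase 3 regimen. With two windows in one SAP section, the programmer has to choose one. If that happens after treatment codes are known, the choice is post hoc. Each rNAPc2 arm has about 40 participants, so a single bleed counted or not counted moves an arm's rate by 2.5 percentage points.

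The liver-test point is separate. A Hy's law screen run as SAP 8.3 is written would have nothing to read for participants whose liver tests exist only in the local-laboratory eCRF. An empty or partial table could then be mistaken for an absence of signals.

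**Working it through.** The plan states no bleeding rate, power or precision for the safety endpoint, so there is no figure to reproduce. The check compares the two windows and then sizes the gap.

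**Step 1. Days lost by discharge day.** SAP 4.3 makes randomization Day 1. Read 8 days from randomization as ending on Day 8, the end-point that SAP 8.1 itself names. For discharge on day *d*, the shorter window ends on min(8, *d* + 2), and days lost = 8 − min(8, *d* + 2).

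| Discharge day | Shorter window ends | 8-day window ends | Days lost |
|---|---|---|---|
| 1 | Day 3 | Day 8 | 5 |
| 2 | Day 4 | Day 8 | 4 |
| 3 | Day 5 | Day 8 | 3 |
| 4 | Day 6 | Day 8 | 2 |
| 5 | Day 7 | Day 8 | 1 |
| 6 or later | Day 8 | Day 8 | 0 |

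**Step 2. Expected bleeds lost.** Arm size is 160 × 1/4 = 40 per rNAPc2 regimen, or 80 pooled. Assumptions, because the documents give none of these:
- early-discharge share *f* = 5–20%;
- 8-day bleeding risk *p* = 2.5–10%, at a constant daily rate;
- mean days lost *m* = 2 (discharge spread evenly over Days 3–5: (3 + 2 + 1)/3) or 3 (all on Day 3).

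Expected loss = N × *f* × *p* × *m*/8.
- Low, N = 40: 40 × 0.05 × 0.025 × 2/8 = 0.0125.
- High, N = 40: 40 × 0.20 × 0.10 × 3/8 = 0.30.
- N = 80: 0.025 to 0.60.

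For an arm of 40 this shifts the expected rate by 0.0125/40 = 0.03 to 0.30/40 = 0.75 percentage points.

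**Step 3. Stress case.** Let 40% leave, spread evenly over Days 2–5. Mean days lost are (4 + 3 + 2 + 1)/4 = 2.5. The share of 8-day person-time lost is 0.40 × 2.5/8 = 12.5%. At a 10% risk, the expected loss is 40 × 0.10 × 0.125 = 0.5 bleeds per arm.

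**Step 4. Against sampling error.** Exact 95% intervals for an arm of 40 are 0.6–16.9% for 2 events (5.0%) and 1.6–20.4% for 3 events (7.5%). The window effect is small beside these.

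**Step 5. The on-treatment scope.** The SAP does not say how discontinuation is dated. If it is dated to the last rNAPc2 dose, adding 3 days ends the scope on Day 4, 6 or 8 for a last dose on Day 1, 3 or 5. A full course on schedule loses nothing.

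**Step 6. Liver tests.** Central results are absent from current Table 2b. The V6.00 change log (07 Jul 2021) records their removal, which is why some earlier participants may have central values. The SAP revision history cites a submission of 29 Nov 2021, so the label in SAP 8.3 postdates the change. The documents do not say how many participants enrolled under each version.

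**The case against.** The strongest reply is that little turns on the window. Exclusion criterion 6 keeps out patients expected to leave within 5 days, the table has no test attached, and the expected loss is below one event per arm even in the stress case. That stands. Ending follow-up shortly after discharge is also a defensible on-treatment definition, because protocol 6.1.2 permits standard-of-care thromboprophylaxis after early discharge. That too stands, and is a reason to keep the shorter count as a sensitivity analysis. Protocol 9.4.1 lets the SAP override the protocol on analysis, but this cannot decide between two sentences of the same SAP section.

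A reader might infer two stronger points that the documents do not support.

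*That the 72-hour scope truncates the primary endpoint.* SAP 5.2 presents that scope as the usual one for safety endpoints, not a universal one. SAP 4.2 lets a specific section override general conventions, although it sits under display conventions. SAP 8.1 states its own window. What remains is a conforming edit.

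*That non-major clinically relevant bleeds will go unadjudicated, or drop out of the primary endpoint.* Protocol 8.3 requires adjudication of major bleeds but does not exclude other bleeds. SAP 8.2.3 refers to positively adjudicated endpoints in terms that include all bleeding, and protocol 9.4.4 refers to adjudicated bleeding without restriction. The CEC charter is not among the documents and may cover these bleeds. It is true that "The study site will know the treatment assignment", but the same protocol section asks that investigators assessing safety events be blinded where possible. This is a point to clarify, not a shown defect.

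On liver tests, the fair reply is that local values are recorded only when the hospital runs them, so changing the source will not give complete coverage. That stands as a limitation.

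**Conclusion.** Two defects hold on current text.

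- **Window.** SAP 8.1 defines the primary safety endpoint in two ways, and only the 8-day version matches SAP 2.4.2 and protocol sections 3 and 4.1. The effect is confined to discharge on or before Day 5 and is probably well under one bleed per arm of 40. That size rests on the assumed discharge shares, bleeding risks and constant rate above. The case for fixing it is that a primary endpoint should be defined once, before unblinding, rather than that the result is likely to change.
- **Liver tests.** A central-only summary under SAP 8.3 would miss participants enrolled after V6.00 took effect. The number cannot be computed from the documents.

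The adjudication wording needs reconciling, but without the CEC charter it cannot be called an error.

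**What to change.** 1. **SAP 8.1.** State one window, matching SAP 2.4.2 and protocol section 3: all qualifying bleeds from randomization through study Day 8, in the Safety population, regardless of discharge or discontinuation. Naming Day 8 also settles whether 8 days from a Day 1 randomization ends on Day 8 or Day 9. Make a conforming edit to the opening of Section 8. Report the discharge-plus-two-days or on-treatment count as a sensitivity analysis; if the latter, say how discontinuation is dated.
2. **SAP 8.3.** Use the AST, ALT and bilirubin values in the local-laboratory eCRF, plus any central values already collected. State that local tests are unscheduled, so coverage will be irregular, and give the number of participants with values.
3. **Clarification in SAP 8.1 and 8.2.1.** If the CEC charter covers non-major clinically relevant bleeds, cite it. If not, show CEC-adjudicated major bleeds and investigator-classified non-major clinically relevant bleeds separately.

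The cost is SAP wording and programming. SAP 8.2.1 already reports bleeding through Day 30, and protocol 8.1.2 already sends local liver tests to the eCRF, so no new data are needed. The labelled split in item 3 adds no CEC work. The price of the single window is that some bleeds after early discharge may occur on standard-of-care thromboprophylaxis; the sensitivity count shows how much that matters.

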9.4.4 SAFETY ANALYSES

Incidence rates of AEs including adjudicated bleeding events, all, serious, fatal, severe and treatment-related AEs reported throughout the conduct of the study will be tabulated by preferred term and system organ class.

Changes in laboratory values and vital signs will be summarized with descriptive statistics. The incidence of concomitant medications will also be summarized.

Drop in hemoglobin level as reported per local laboratory data will be used as an indicator of potential bleeding risk.

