The ASPEN-COVID-19 ("ASPEN") protocol comprises sequential Phase 2b and Phase 3 randomized, multicenter, active comparator studies evaluating the hypothesis that rNAPc2, a novel, potent and highly selective tissue factor inhibitor with anticoagulant, anti-inflammatory and potential antiviral properties, reduces elevated D-dimer levels (Phase 2b primary endpoint) and shortens time to recovery (Phase 3 primary endpoint) compared to heparin in hospitalized patients with COVID-19 and elevated D-dimer levels. Study participants and Clinical Endpoint Committee (CEC) members assessing the clinical endpoints are blinded to treatment assignment. Analysis of Phase 2b data could lead to study discontinuation, adjustment of eligibility criteria or sample size, and will inform the rNAPc2 dose regimen to be studied in Phase 3.

This statistical analysis plan (SAP) describes all study related details and statistical analyses and summaries to be generated on data collected from the Phase 2b ASPEN-COVID-19 study.

The SAP is designed to assist in the analysis of clinical study data for final reporting of the Phase 2b study. This content includes, but is not limited to, statistical analysis and summary of all endpoints identified in the study protocol, heretofore referred to as 'the study' or 'study.'

Details of reporting for the purpose of the Data Safety Monitoring Committee (DSMC) and other committees are documented elsewhere. Details of planned interim analyses are documented in the DSMC Charter and DSMC Reporting Plan. Reporting of the Phase 3 study will be documented in a separate analysis plan.

2 Study Design and Plan

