11.4 Additional Safety Analyses

Decrease in hemoglobin level reported by local laboratories will be monitored to be used as an indicator of potential bleeding risk. As a variable, decrease will be dichotomized such that a decrease of more than 3 g/dL will constitute an event, and any decrease of less than 3g/dL will constitute a non-event. To provide the broadest view of potential bleeding risk, heparin treated subjects will be considered together regardless of prophylactic or therapeutic regimens. The rNAPc2 subjects will be stratified with regard to regimen received. A Cochran Mantel Haenszel Test with stratification will be performed to examine the frequency of events and non-events across the two treatment groups.

12 Changes from Methods Planned in the Protocol

Wilcoxon Signed Rank will not be used in the analysis of the primary efficacy endpoint.

Probability of discharge as assessed by ACTT ≥ 6 by Day 8 and Day 30 post randomization is now a secondary efficacy endpoint.

Composite of death, thrombosis, organ support, or rehospitalization within 30 days is now a secondary efficacy endpoint.

Rehospitalizations and their relatedness to COVID-19 will be adjudicated.

13 References

14 Appendix

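### The primary safety endpoint is defined relative to heparin, but the SAP plans only percentages by arm, with no between-arm estimate or confidence interval for bleeding

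*SAP*

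**What the plan says.** SAP 2.4.2 states the primary safety endpoint as "major or non-major clinically relevant bleeding within eight (8) days of randomization as compared to heparin". Protocol section 3 gives the same endpoint and sets the Phase 2b safety objective: to "identify an rNAPc2 dosing regimen with an acceptable bleeding profile compared to SoC heparin regimens". The comparison is therefore part of both the endpoint and the objective.

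The planned analysis is in SAP 8.1: "The frequency and percentage of participants with major or non-major clinically relevant bleeding within 8 days of randomization", as adjudicated, "will be presented by each rNAPc2 dose and any heparin dose". SAP 8.2.1 and 8.2.2 plan the same kind of summary for the secondary bleeding endpoints, with heparin also split by intensity and type. Protocol 9.4.4 says that adverse events, including adjudicated bleeding, "will be tabulated by preferred term and system organ class".

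One between-arm safety analysis is planned. In SAP 11.4, for a hemoglobin decrease of more than 3 g/dL on local laboratory values, "A Cochran Mantel Haenszel Test with stratification will be performed".

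**The concern.** With about 40 participants per dose, an observed percentage is imprecise, and the difference between two such percentages is more so. A table of percentages shows the point values but not the range of true differences that the data allow. The Phase 2b data are meant to inform the rNAPc2 regimen taken into Phase 3 (SAP section 1, protocol 9.4.8), and bleeding relative to heparin is one of the two criteria in the primary objective. If similar percentages appear without an interval, nothing in the planned output tells the reader how large an excess of bleeding remains possible. If a dose shows a higher percentage, nothing tells the reader how firmly that is established.

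**Working it through.** **Step 1. Is an estimate or interval assigned to bleeding anywhere else?**

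- SAP 7.4 sets a two-sided 0.05 convention for whatever tests and intervals are run. It sits in the efficacy section and assigns none to bleeding.
- SAP section 10 lists mortality, thrombotic events, organ support and rehospitalization as its composite/net outcome. Bleeding is not a component.
- SAP 11.4 tests a hemoglobin decrease, which is a different variable.
- SAP section 12 records no change that would supply a bleeding comparison.
- The DSMC charter and reporting plan cover interim reporting. For Phase 2b as a whole, SAP section 1 says that the SAP "describes all study related details and statistical analyses and summaries to be generated on data collected from the Phase 2b" study.

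So none is assigned.

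**Step 2. Inputs for an illustration.**

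- Denominators: about 160 randomized 1:1:2 (SAP 2.2), so 160/4 = 40 per rNAPc2 dose, 80 pooled, and 80 on heparin. This assumes that every randomized participant is treated as allocated.
- Rates: neither document gives an expected rate, margin or power for this endpoint, so there is no figure of the plan's own to reproduce. Rates of 2.5% to 10% are assumed. As a loose guide only, protocol 2.2 reports major bleeding of 0, 3.4% and 10.6% by dose after knee replacement, and 3.7% vs 2.5% in acute coronary syndrome.

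**Step 3. Method.** For each arm, the Wilson 95% limits l and u are [p + z²/2n ± z√(p(1−p)/n + z²/4n²)] / (1 + z²/n), with z = 1.96. The Newcombe limits for d = p1 − p2 are

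- lower = d − √[(p1 − l1)² + (u2 − p2)²]
- upper = d + √[(u1 − p1)² + (p2 − l2)²]

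Wilson limits in percent: 2/40 gives 1.38 to 16.50; 4/40 gives 3.96 to 23.05; 4/80 gives 1.96 to 12.16.

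**Step 4. Three cases worked through (percentage points).**

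- One dose, 2/40 vs 4/80: lower = 0 − √(3.62² + 7.16²) = -8.0; upper = 0 + √(11.50² + 3.04²) = +11.9.
- Pooled, 4/80 vs 4/80: limits = ±√(3.04² + 7.16²) = ±7.8.
- One dose, 4/40 vs 4/80: lower = 5 − √(6.04² + 7.16²) = -4.4; upper = 5 + √(13.05² + 3.04²) = +18.4.

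**Step 5. Sensitivity to the assumed rate.**

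| Observed rates | One dose (n=40) vs heparin (n=80) | Pooled (n=80) vs heparin (n=80) |
|---|---|---|
| 2.5% vs 2.5% | 0.0 (-6.5 to +10.5) | 0.0 (-6.4 to +6.4) |
| 5% vs 5% | 0.0 (-8.0 to +11.9) | 0.0 (-7.8 to +7.8) |
| 10% vs 10% | 0.0 (-10.4 to +13.9) | 0.0 (-9.8 to +9.8) |
| 10% vs 5% | 5.0 (-4.4 to +18.4) | 5.0 (-3.6 to +14.0) |

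Identical percentages leave an excess of about 10 to 14 points possible for one dose, and about 6 to 10 points for the pooled doses.

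**Step 6. Would a test serve better?** At two-sided 0.05, power to detect 10% vs 5% is about 20% for one dose and 22% pooled. A non-significant result would say little, so an interval is the more useful output.

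**The case against.** Descriptive safety reporting looks like a deliberate and consistent choice. Protocol 9.1 states hypotheses only for efficacy, protocol 9.4.4 plans tabulation, and SAP 8.1 and 8.2 follow it. For a Phase 2b trial of this size that is defensible. It answers a demand for a test, but not the absence of an estimate for an endpoint that is worded as a comparison.

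A reader might infer that the plan makes no comparison with heparin at all. The documents do not support that. SAP 8.1 sets each dose beside heparin, and SAP 4.2 puts group sizes in the column headings with counts in the cells. An informal comparison is possible, and anyone could compute the interval from the planned table. The gap is that the estimate and its uncertainty are neither pre-specified nor shown.

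A reader might also infer from the hemoglobin test in SAP 11.4 that the primary safety endpoint needs a test. It does not follow. The contrast shows uneven planning, no more. Nor does any text say that equal percentages will be read as equal safety; that is a risk in interpretation, not something the plan states.

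Two limits stand. No threshold for acceptable bleeding is given, so an interval informs the judgment but does not settle it. The numerator also needs attention. SAP 8.1 gives two windows (one ends two days after an early discharge, the other is eight days from randomization), on top of the on-treatment scope in SAP 5.2. It also treats non-major clinically relevant bleeding as centrally adjudicated, whereas protocol 8.3 specifies central adjudication only for major bleeding.

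**Conclusion.** The point holds as a gap in estimation and reporting. The primary safety endpoint is comparative by definition, and the plan assigns it no between-arm estimate or interval. Under the assumed rates and full 40/40/80 denominators, equal observed rates of 5% would still be compatible with up to 11.9 points more bleeding on one dose than on heparin, or 7.8 points for the pooled doses, and the planned table would not show this. The exact limits depend on rates that the documents do not give and on actual numbers in the Safety population. The conclusion that the intervals are wide holds across the assumed range. The finding does not imply that the trial needed a powered bleeding comparison, or that safety data are missing.

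**What to change.** In SAP 8.1 and 8.2.1, add the risk difference with a two-sided 95% confidence interval (Newcombe or Miettinen-Nurminen; name one) for three contrasts: each rNAPc2 dose vs all heparin, and pooled rNAPc2 vs all heparin. The pooled group is already defined in SAP 4.5 as ALL rNAPc2, although SAP 8.1 does not name it. Use the Safety population, and label the intervals as estimation with no hypothesis test. Specify them before unblinding, and report them when the Phase 2b data are used to identify the Phase 3 regimen (protocol 9.4.8). In the same edit, reconcile the event window in SAP 8.1, and the adjudication rule between SAP 8.1 and protocol 8.3, so that the numerator is unambiguous.

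For the estimates themselves the cost is a few table columns, with no new data and no use of alpha. The downside is that wide intervals will make the safety conclusion look less certain than percentages alone, which is an accurate picture at this sample size.
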